10. STATISTICS

Any data analysis carried out independently by the investigator should be submitted to the sponsor before any publication or presentation.

Data from all the sites and centers will be combined in the efficacy and safety analysis.

10.1. Sample Size Determination

The primary objective of the study is to detect a statistically significant difference in PFS (INV) for the tafasitamab-lenalidomide combination in addition to rituximab relative to placebo-lenalidomide in addition to rituximab for participants with FL.

Based on the assumptions in Table 12 below, a total number of 174 PFS events in the FL population are required to detect a HR of 0.65 with 80% power at the primary analysis, using a 2-sided log-rank test at an alpha level of 5% and a 1:1 randomization ratio between the 2 treatment groups. Assuming a median PFS of 27.8 months for lenalidomide in addition to rituximab (TGB), 21 months of enrollment, 12 months of follow-up for PFS, and 15% of dropouts, 528 evaluable FL participants need to be randomized.

Table 12: Sample Size Assumptions

Primary endpoint	Progression-free survival (INV) for the FL population
Median PFS in TGA	42.8 months
Median PFS in TGB	27.8 months
Randomization ratio	1:1
Assumed HR	0.65
Alpha (2-sided)	5%
Power	80%
Enrollment duration	21 months
Follow-up for PFS (starting from last participant randomized)	12 months
Accrual rate	0.1 participant/site/month
PFS events required at primary analysis	174
Total participants (without dropout)	448
Assumed dropout rate	15%
Total randomized participants	528

A minimum of 60 and up to 90 additional participants with MZL will be randomized at a 1:1 ratio to one of the 2 treatment groups. The number of MZL participants is based on an expected enrollment proportion of FL and MZL participants.

A 2-stage design with 1 interim analysis for a potential futility stop will be applied. Information regarding the stopping boundaries at the interim and primary analyses is provided in Section 10.4 and Section 10.5.

10.2. Population for Analysis

A full description of the population for analysis is presented in Table 13.

Table 13: Analysis Population

Population	Description
All screened	All participants who sign the ICF.
FAS	All randomized participants. Treatment groups for this population are determined according to the treatment they have been assigned at the time of randomization. The FAS will be used for the summary of demographics, baseline characteristics, participant disposition, and analyses of all efficacy data.
PPS	The subset of the participants in the FAS who are compliant with the requirements of the clinical study Protocol. All Protocol deviations or conditions leading to exclusion from the PPS will be detailed in the Protocol Deviation Specifications. Sensitivity analyses of the primary endpoint may be performed using PPS.
SAF	All randomized participants who receive at least 1 dose of tafasitamab/placebo, lenalidomide, or rituximab. Treatment groups for this population will be determined according to the actual treatment the participant received on Cycle 1 Day 1 regardless of assigned treatment at the time of randomization. All safety analyses will be conducted using the SAF.

10.3. Level of Significance

The primary endpoint of PFS in the FL population and 3 key secondary endpoints will be tested with inferential statistics. Hypothesis testing for other secondary and exploratory endpoints may be performed for exploratory purposes. Estimates and p-values will be reported for illustrative and exploratory purpose.

Statistical tests will use a 0.05 significance level and will be 2-sided unless otherwise noted. Confidence intervals, both individual and simultaneous, will be at 95% confidence level unless stated otherwise.

In order to control the study-wise type I error due to the multiple testing of the primary and key secondary endpoints, a hierarchical order of testing will be implemented.

The primary endpoint analysis will serve as a gatekeeper:

• PFS by INV in the FL population

If the primary hypothesis is rejected, the key secondary endpoints can be tested with the following fixed order:

- PFS by INV in the overall population (FL and MZL)
- PET-CR rate by INV in the FDG-avid FL population
- OS in the FL population

If a null hypothesis is not rejected, the formal sequential testing will be stopped, and the p-values for the remaining key secondary endpoints will be reported for exploratory and illustrative purposes.

The primary analysis will be performed after approximately 174 PFS events based on INV are observed in the FL population in the FAS. The primary analysis is independent of the number of enrolled MZL participants. Recruitment will be stopped when the required 528 FL participants for the primary analysis and at least 60 MZL have been randomized. The maximum number of randomized MZL participants is 90. Formal hypothesis testing will not be performed for OS at the time of primary analysis; however, HRs may be estimated.

The final analysis will be performed at the end of the study as defined in Section 8.9.4. At the time of final analysis, the last key secondary endpoint OS will be tested.

Other secondary and exploratory endpoints will be tested using a 2-sided, 5% significance level without multiplicity adjustment. Estimates and nominal p-values will be reported for exploratory purpose. Additional follow-up analyses for safety or efficacy endpoints may be performed if needed or requested by regulatory authorities.

10.4. Statistical Analyses

10.4.1. Efficacy Analyses

All efficacy analyses will be based on FAS.

10.4.1.1. Primary Analysis for Progression-Free Survival in the Follicular Lymphoma Population

Progression-free survival as per INV is defined as the time from the date of randomization to the date of first documented disease progression, as determined by disease assessment per Lugano 2014 criteria, or death due to any cause, whichever occurs earlier.

For a given analysis, PFS will be censored if no PFS event is observed before the cutoff date or on the date that a new antilymphoma therapy is started. Censoring for PFS will follow the algorithm outlined in Table 14, which is based on the FDA Guidance (FDA 2015, FDA 2018).

Table 14: Evaluation and Censoring of Progression-Free Survival for Primary Analysis

Situation	Censoring/Event Time	Outcome	Censoring Reason
No baseline tumor assessment	Date of randomization	Censored	No baseline assessment
No valid postbaseline tumor assessment	Date of randomization	Censored	No postbaseline assessment
No PFS event observed before cutoff	Date of last adequate tumor assessment prior to cutoff date	Censored	Ongoing
Study discontinuation for undocumented progression or other reason	Date of last adequate tumor assessment prior to cutoff date	Censored	Study discontinuation
Start of a new antilymphoma treatment	Date of last adequate tumor assessment on/before start of new antilymphoma treatment	Censored	Start of new antilymphoma treatment
Death or disease progression documented after 2 or more missing or nonadequate tumor assessments	Date of last adequate tumor assessment with overall lesion response of CR, PR, or SD prior to PD	Censored	Death or PD after 2 or more missing assessments

The date of last adequate tumor assessment is the date of the last tumor assessment with overall lesion response of CR, PR, SD. In this case, the last tumor evaluation date at that assessment is used. If a PFS event is observed after a single missing or nonadequate tumor assessment, the actual date of event will be used, as per Cheson et al (2014) criteria.

The distribution of PFS as per INV will be compared between the 2 treatment groups using a stratified log-rank test at 2-sided 5% level of significance. The strata information will be based on the data obtained from the IRT that was used for randomization.

A stratified Cox proportional hazard model will be used to estimate the HR between TGA (tafasitamab-lenalidomide in addition to rituximab) versus TGB (placebo-lenalidomide in addition to rituximab), along with 2-sided 95% CI, using the same stratification factor as for randomization as mentioned in Section 4.1.

The distribution of PFS will be estimated using the Kaplan-Meier method. The median along with 2-sided 95% CIs will be presented by treatment group. In addition, investigator-assessed PFS event rates at 6, 12, 18, 24, 36, and 48 months will be provided along with the corresponding 2-sided 95% CIs for the estimates.

All analysis mentioned above will be performed for participants with FL in the FAS.

If the null hypothesis is rejected at a 2-sided significance level of 5%, the primary endpoint is met. The p-value obtained from stratified log-rank test for PFS in the FL population using the

strata information based on IRT that was used for randomization will be used for hierarchical testing.

In case of discrepancies in the diagnosis between the eCRF and the IRT, the participants will be analyzed into the population based on eCRF diagnosis.

If a participant was randomized into the MZL cohort but after randomization was confirmed by the site to have a diagnosis of FL, the eCRF-derived information for medical history will be used to derive the 2 missing stratification factors for the FL cohort: POD24 status (yes versus no) and refractoriness to prior anti-CD20 mAb therapy (please see the definition in Section 4.1). If a participant was randomized into the FL cohort but after randomization was confirmed by the site to have a diagnosis of MZL, the IRT-derived stratification factor needed for this cohort (number of prior lines of therapy: $< 2 \text{ vs} \ge 2$) will be used.

Additional sensitivity analyses will be performed as mentioned in Section 10.4.1.6.

10.4.1.2. Analyses of Key Secondary Efficacy Endpoints

Hierarchical testing will be implemented for the key secondary endpoints, with the primary endpoint PFS serving as a gatekeeper. This hierarchical testing procedure will maintain the study-wise Type I error.

10.4.1.2.1. Progression-Free Survival in the Overall Population

Progression-free survival in the overall population (FL and MZL) will be compared and analyzed in the same manner as described above in Section 10.4.1.1 for the PFS in the FL population. The strata information for the stratified log-rank test will be based on the randomization factor used for both cohorts, FL and MZL: number of prior lines of therapy ($< 2 \text{ vs} \ge 2$).

The p-value obtained from the stratified log-rank test for PFS in the overall population using the strata information based on IRT that was used for randomization, including stratification by FL versus MZL, will be used for hierarchical testing.

Additional

sensitivity analyses will be performed as mentioned in Section 10.4.1.6.

10.4.1.2.2. Positron Emission Tomography—Complete Response Rate in the FDG-Avid Follicular Lymphoma Population

The PET-CR rate is defined as the proportion of participants who achieved a CR as per Lugano classification (Cheson et al 2014) with a PET-negative result among the participants with a positive PET scan at baseline. Participants with a positive PET scan are defined as participants with a Deauville score of 4 or 5.

Participants with no postbaseline assessment by PET or who did not achieve a PET-CR will be classified as "non CR-responder."

The CR rate will be compared between the 2 treatments groups using stratified CMH test using the same stratification factor as for randomization as for the PFS primary analysis. The odds ratio and its 95% CIs calculated from the stratified CMH test will also be presented. The number

of participants classified as PET-CR responders and the respective rates as well as 95% CIs (using Clopper-Pearson) will be presented.

Key secondary analysis of PET-CR will be performed for participants with FDG-avid FL in the FAS.

If the null hypothesis is rejected at a 2-sided significance level of 5%, this key-secondary endpoint is met. The p-value obtained from CMH test for PET-CR rate as per INV observed in the FDG-avid FL population using the strata information based on IRT that was used for randomization will be used for hierarchical testing.

Additional sensitivity analyses will be performed as mentioned in Section 10.4.1.6.

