10.4.1.4. Analyses of Other Secondary Efficacy Endpoints

10.4.1.4.1. Positron Emission Tomography-Complete Response Rate in the Overall Population

The PET-CR rate in the overall FDG-avid population (FL and MZL) will be compared and analyzed in the same manner as described in Section 10.4.1.2.2 for the PET-CR rate in the FDG-avid FL population. The stratification factors will be those used for the PFS analysis on

the FL population and on the overall population, respectively (see Section 10.4.1.1 and Section 10.4.1.2.1).

10.4.1.4.2. Minimal Residual Disease-Negativity Rate at End of Treatment in the Follicular Lymphoma and Overall Population

The MRD-negativity rate is defined as the proportion of participants who achieved a negative MRD result at EOT. Participants with no postbaseline assessment or who did not achieve a negative MRD result will be classified as "non MRD-negative."

The MRD-negativity rate in the 2 treatment groups will be compared and analyzed in the same manner as described in Section 10.4.1.2.2 for the PET-CR rate. The stratification factors will be those used for the PFS analysis on the FL population and on the overall population, respectively (see Section 10.4.1.1 and Section 10.4.1.2.1). Analysis of the MRD-negativity rate at EOT will be performed for participants with FL and the overall population (FL and MZL) in the FAS.

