10.4.1.4.5. Overall Survival in Overall Population

Overall survival in the overall population (FL and MZL) will be compared and analyzed in the same manner as described in Section 10.4.1.2.3 for the OS in the FL population. The only difference will be that the strata information for the stratified log-rank test will be based on the randomization factor used for both cohorts, FL and MZL: number of prior lines of therapy ($< 2 \text{ vs} \ge 2$).

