7.3.2.1. Progression-Free Survival in the Overall Population

Progression-free survival by INV assessment in the overall population (FL and MZL) will be compared and analyzed in the same manner as described in Section 7.3 for the PFS in the FL population. The strata information for the stratified log-rank test will be based on the randomization factor used for both cohorts, FL and MZL: number of prior lines of therapy ($< 2 \text{ versus} \ge 2$).

The p-value obtained from the stratified log-rank test for PFS in the overall population, using the strata information based on IRT that was used for randomization, as well as stratification by FL versus MZL, will be used for hierarchical testing.

As mentioned in Section 7.3, participants with different initial diagnosis by INV and in the IRT will be considered as mentioned in the eCRF.

7.3.2.2. Positron-Emission Tomography-Complete Response Rate in the FDG-Avid Follicular Lymphoma Population

The PET-CR rate is defined as the proportion of FDG-avid participants who achieved a CR as per Lugano classification (Cheson et al 2014) with a PET-negative result defined as a complete metabolic response at any time after start of treatment over the FDG-avid FL population at baseline. FDG-avid FL participants with no postbaseline assessment by PET or those who did not achieve a PET-CR will be classified as "non-CR-responder."

The CR rate will be compared between the 2 treatments groups using a stratified CMH test. The odds ratio and its 95% CIs calculated from the stratified CMH test will also be presented. The number of participants classified as PET-CR responders and the respective rates as well as 95% CIs (using Clopper-Pearson) will be presented.

Analysis of the key secondary endpoint of PET-CR will be performed for participants with FDG-avid FL in the FAS. If the null hypothesis is rejected at a 2-sided significance level of 5%, this key secondary endpoint is met. The p-value obtained from the CMH test for PET-CR rate by INV assessment in the FDG-avid FL population, using the strata information based on IRT that was used for randomization, will be used for hierarchical testing.

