7.4. Analysis of Other Secondary Efficacy Parameters

7.4.1. Positron-Emission Tomography-Complete Response Rate in the FDG-Avid Overall Population

The PET-CR rate in the FDG-avid overall population (FL and MZL) will be compared and analyzed in the same manner as described in Section 7.3.2.2 for the PET-CR rate in the FDG-avid FL population.

7.4.2. Minimal Residual Disease-Negativity Rate at End of Treatment in the MRD-Evaluable Follicular Lymphoma Population and MRD-Evaluable Overall Population

The MRD-negativity rate is defined as the proportion of participants who achieved a negative MRD result in peripheral blood at the EOT. The threshold used for the analysis is 10^{-5} cells. Participants with no postbaseline assessment, or who did not achieve a negative MRD result will be classified as "non–MRD-negative." Analysis of the MRD-negativity rate at EOT will be performed for participants in the MRD-blood evaluable FL population and the MRD-blood evaluable overall population (FL and MZL).

The MRD-negativity in the 2 treatment groups will be compared and analyzed in the same manner as described in Section 7.3.2.2 for the PET-CR rate.

The MRD analysis will be performed using samples with a time interval of ≤ 5 days between sample collection and receipt by the laboratory to ensure sample integrity.

Reasons for missing MRD assessments will be summarized, for example, missed assessment, unevaluable assessment.

Sensitivity analysis will be performed on:

- Using peripheral blood sample at both C4 and C8 (in the MRD-blood evaluable population)
- Using bone marrow sample at EOT (in the MRD-bone marrow evaluable population)
- Using bone marrow sample at CR (in the MRD-bone marrow evaluable population)

Estimates of the MRD-negativity rate along with its exact 95% CIs using the Clopper-Pearson method will be calculated for each treatment group. No statistical comparison will be performed for this analysis.

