7.4.5. Overall Survival in Overall Population

Overall survival in the overall population (FL and MZL) will be compared and analyzed in the same manner as described in Section 7.3.2.3 for the OS in the FL population. The only difference will be that the strata information for the stratified log-rank test will be based on the randomization factor used for both cohorts, FL and MZL: number of prior lines of therapy ($< 2 \text{ versus} \ge 2$).

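### Strata for the overall-population PFS test are not uniquely defined; the likeliest reading leaves out POD24 and anti-CD20 refractoriness, at a small cost in power

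*Protocol*

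**What the plan says.** FL and MZL participants are randomised separately (Protocol 4.1 and 6.3, SAP 3.1). FL uses POD24, refractoriness to prior anti-CD20 therapy and number of prior lines. MZL uses prior lines only.

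For overall PFS, Protocol 10.4.1.2.1 refers back to the FL analysis and then says: "The strata information for the stratified log-rank test will be based on the randomization factor used for both cohorts, FL and MZL", naming prior lines. The next paragraph says that the p-value for the hierarchy uses "strata information based on IRT that was used for randomization, including stratification by FL versus MZL". SAP 7.3.2.1 repeats both statements, the second as "using the strata information based on IRT that was used for randomization, as well as stratification by FL versus MZL".

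The FL analysis that overall PFS follows (Protocol 10.4.1.1) fits its Cox model "using the same stratification factor as for randomization as mentioned in Section 4.1". SAP 7.3.1 names no strata for the Cox model, so the default in SAP 7.1, the IRT randomisation factors, applies.

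Other overall-population endpoints differ again:

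- **OS.** Prior lines alone, with no mention of FL versus MZL as a stratum. Protocol 10.4.1.4.5 says "the strata information for the stratified log-rank test will be based on the randomization factor used for both cohorts, FL and MZL", and SAP 7.4.5 says "The only difference will be that the strata information for the stratified log-rank test will be based on the randomization factor".
- **PET-CR, MRD and ORR.** Protocol 10.4.1.4.1 to 10.4.1.4.3 point to the PFS strata: "The stratification factors will be those used for the PFS analysis on the FL population and on the overall population, respectively". SAP 7.4.1 to 7.4.3 point instead to the FL PET-CR analysis, which uses the randomisation strata; for PET-CR, the overall analysis "will be compared and analyzed in the same manner as described in Section 7.3.2.2 for the PET-CR rate in the FDG-avid FL population".

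**The concern.** Overall PFS carries alpha. If it fails, PET-CR and OS in FL cannot be tested formally. A gating test needs one prespecified statistic, and the estimate reported beside it should come from the same strata. Here two programmers could each follow the text and produce different p-values, or a p-value from one set of strata and a hazard ratio with its interval from another.

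The natural reading of the p-value text also sets aside POD24 and refractoriness, which the primary FL analysis uses. If these factors are prognostic for PFS, the test loses some power. The overall hazard ratio would also be conditioned on less than the FL hazard ratio and sit slightly closer to 1. That is non-collapsibility, not bias, but the two estimates would not be like for like.

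**Working it through.** **1. The plan's own figure.** Inputs from Protocol Table 12: HR 0.65, two-sided 5%, 80% power, 1:1 allocation.

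- Schoenfeld: 4(1.96 + 0.84)² / (ln 0.65)² = 169.2, so 170 events.
- Freedman: (1.96 + 0.84)² × (1.65/0.35)² = 174.4.
- Sample size: 448/0.85 = 527.1, so 528.

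The stated 174 events and 528 participants reproduce.

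**2. The strata each text implies.**

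| Text | Applies to | Strata |
|---|---|---|
| Protocol 10.4.1.2.1 and SAP 7.3.2.1, shared-factor sentence | log-rank test | prior lines: 2 |
| Same sections, hierarchy sentence | p-value for the hierarchy | prior lines × FL/MZL: 4; or all randomisation cells: 2×2×2 + 2 = 10 |
| Protocol 10.4.1.1 by reference; SAP 7.1 default | Cox hazard ratio and CI | all randomisation cells: 10 |

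The FL share of the population is 528/618 = 85% to 528/588 = 90%.

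**3. Events for the overall test.** If MZL has the same event rate as FL, 60, 75 or 90 MZL participants give 174 × 588/528 = 194, 174 × 603/528 = 199, or 174 × 618/528 = 204 events. Schoenfeld power, Φ(√d × |ln 0.65|/2 − 1.96), is 85.0%, 85.9% and 86.7%.

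**4. Power of 4 strata against 10 cells, by simulation.**

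- From the documents: 528 FL, 75 MZL (midpoint of 60 to 90), 21-month accrual, 15% dropout, FL medians 27.8 and 42.8 months at HR 0.65, cutoff at the 174th FL event.
- Assumed: exponential times, POD24 35%, refractory 40%, two or more prior lines 45%, prior-lines HR 1.3, and the prognostic HRs in the table.
- 20,000 trials per row, with both tests run on the same data.

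| PFS HR for POD24 / refractoriness | HR 0.65: 4 strata / 10 cells | HR 0.70: 4 strata / 10 cells |
|---|---|---|
| 1.0 / 1.0 | 85.6 / 85.4 | – |
| 1.25 / 1.25 | 84.9 / 84.8 | – |
| 1.5 / 1.25 | 84.8 / 84.9 | 70.2 / 70.5 |
| 1.5 / 1.5 | 84.4 / 84.9 | 69.1 / 69.8 |
| 2.0 / 1.5 | 83.8 / 85.0 | 67.4 / 69.0 |
| 2.5 / 2.0 | 81.8 / 84.9 | 65.0 / 69.3 |

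- Prior lines alone is within 0.2 points of 4 strata.
- With POD24 prevalence at 20%, the background figure in Protocol 2.1.4.2, the gain at 2.0/1.5 is +0.9 instead of +1.2.
- Joint success on FL PFS and overall PFS goes from 78.6/78.6 (1.0/1.0) to 76.6/78.7 (2.5/2.0) at HR 0.65, and from 61.5/61.9 (1.5/1.25) to 58.4/61.2 (2.5/2.0) at HR 0.70.
- The two tests fall on opposite sides of 5% in 1.8 to 4.6% of trials at HR 0.65 and 3.0 to 6.5% at HR 0.70.

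**5. Validity and the estimate.** With no treatment effect and prognostic HRs 2.5/2.0, two-sided rejection is 4.1% (4 strata) and 5.1% (10 cells). At true HR 0.65 the mean estimate ranges over 0.649 to 0.668 (4 strata) and 0.649 to 0.651 (10 cells).

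**6. A second simulation with different settings.** It used blocks of 4, 60 or 90 MZL, POD24 prevalence 20 to 40%, and an MZL/FL hazard ratio of 0.8 to 1. Prognostic HRs are for POD24/refractoriness/prior lines. Power for 4 strata against 10 cells at HR 0.65:

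- none: 84.7–87.3 against 84.1–86.9
- 1.5/1.5/1.3: 83.1–83.8 against 83.3–84.0
- 2/2/1.5: 79.4–83.4 against 82.0–85.0
- 3/2/1.5: 76.3–79.7 against 81.4–83.6

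One-sided error was 0.018 to 0.027 across all the strata choices tried, against 0.025.

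**7. Overall OS (no alpha).** With control median 120 months and HR 0.65 (SAP Table 15), cut at 96 months, prior lines alone against 10 cells gives 82.8/83.1, 82.2/83.7 and 80.6/84.1 for POD24/refractoriness HRs of 1.5/1.25, 2.0/1.25 and 3.0/1.5. Adding only FL/MZL changes power by at most 0.3 points.

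**The case against.** The two paragraphs of Protocol 10.4.1.2.1 can be read together: the first gives the shared factor and the second adds FL versus MZL. The SAP wording is additive, and the 10-cell reading would make the shared-factor sentence pointless. SAP 10.2.1 records that Sections 7.3.2.1 and 7.4.5 were revised to clarify the stratification factors, so the choice looks deliberate. It is also coherent, because POD24 and refractoriness are FL-only factors. The Cox wording in 10.4.1.1 describes the FL analysis. The planned test is valid. The larger gains need prognostic HRs that no document supports: Protocol 2.1.4.2 gives POD24 as prognostic for OS, not PFS. Two valid, highly correlated tests will disagree now and then whichever is better. The other overall-population endpoints carry no alpha.

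Much of this stands. Prior lines by FL/MZL is the natural reading of the p-value text, the power cost is small, and the disagreement rate shows only that the choice can matter, not that one choice is harmful. What remains is that neither document names the Cox strata for the overall population, and the only text that reaches them points to the full randomisation factors. Reading the p-value sentence clearly also confirms that POD24 and refractoriness are left out.

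**Conclusion.** The concern holds, as a minor improvement to the plan and not an error that threatens it. The strata for an alpha-controlled test are not listed, the p-value and hazard ratio can rest on different strata, and the natural reading omits two factors by which 85 to 90% of the population is randomised. Type I error is not inflated; the 4-strata test is slightly conservative when the omitted factors are prognostic.

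At HR 0.65 the main simulation puts the power change at -0.2 to about +3 points, and under 1 point up to prognostic HRs of 1.5/1.5. At HR 0.70 it is +0.3 to +4.3. The second simulation reaches 4 to 6 points only with a POD24 PFS hazard ratio near 3. These sizes depend on assumed prevalences and, above all, assumed prognostic effects on PFS. The gap in the wording does not depend on them.

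**What to change.** In Protocol 10.4.1.2.1 and 10.4.1.4.5 and SAP 7.3.2.1 and 7.4.5, state one set of strata for both the log-rank test and the Cox model. The preferred set is 8 FL cells (POD24 × refractoriness × prior lines) plus 2 MZL cells (prior lines). Use IRT values and keep the existing rule for discordant diagnoses: the eCRF diagnosis decides the cohort, and FL factors missing from the IRT are derived from the eCRF. Align Protocol 10.4.1.4.1 to 10.4.1.4.3 and SAP 7.4.1 to 7.4.3 so that overall PET-CR, MRD and ORR use the same strata.

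If the sponsor prefers prior lines by FL/MZL, say so explicitly for both the p-value and the hazard ratio, and say whether overall OS also includes FL/MZL.

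The cost is a text change in both documents, to be made before unblinding; the documents supplied do not show whether that has happened. The data are already in the IRT and eCRF, and the 8 FL cells already serve the primary analysis. In the main simulation the 10 cells cost at most 0.2 points of power when the two factors have no effect. No participants or visits are added.
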